12. DATA COLLECTION

12.1. Study Design:

This is a non-randomized Phase II pilot protocol to determine the feasibility, toxicity, and disease control (overall and progression-free survival) using SBRT in patients with pulmonary oligometastatic disease from soft tissue sarcoma primaries.

12.2. Primary Endpoint:

The primary aim of this study is to assess toxicity and quality of life from SBRT. All patients will be followed for the primary endpoint for a minimum of 3 years. Based on historical data, we expect there will be minimal toxicity, both acute and long term. Adverse event rates will be compared at specific time points (3, 6 and 12 months after completion of SBRT). Quality of life will be measured with the FACT-L questionnaire (Appendix IV).

12.3. Secondary Endpoint:

The secondary objective of this study is to assess local and regional control, progression-free survival and overall survival. Local and regional recurrence will be defined for each lesion per criteria in section 11.3.2. Disease-free survival is defined as the time from randomization until documented disease-recurrence or death, whichever occurs first. Patients who are disease-free and alive at the time of analysis will be censored at the time of their last follow-up. Patients will be followed for disease-free survival for a minimum of 3 years.

12.4. Endpoint Analysis:

Crude rates of locoregional recurrences will be documented as well as the time to development of recurrence or relapse. Time of last follow-up or death will also be noted. This will allow us to calculate progression free and overall survival rates.

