11.0 PATIENT ASSESSMENTS

11.1 Study Parameters

Assessments	Pre-Study Entry	During Therapy (each fraction)	At 4-6 Weeks (+/- 1 month) after SBRT	Every -6 months (+/- 1 month) after RT for 12years
History/physical,	X		X	X
Zubrod PS	X	X	X	X
Toxicity Evaluation		X	X	X
QoL (FACT-L)	X			X
CT of the Chest	X*			X
PET/CT	X**			If Needed***
PFTs	X (not required)			X** (not required)

PFTs are not required for this protocol. PFTs may be done pre-treatment and 3 months after therapy and as clinically indicated.

*CT scan- within 6-8 weeks of study entry

** PET/CT -may be omitted if not covered by insurance although is recommended to assist in treatment planning and to assess the appropriateness of study therapy.

***PET/CT-to be done at discretion of physician

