11.2 PATIENT ASSESSMENTS

11.2.1 Patients will be seen 4 to 6 weeks after the last fraction of radiation therapy, every 6 months for 2 years.

11.2.2 Prior to each visit, a CT of the chest with contrast will be obtained for disease assessment. If there is deemed to be progressive disease, a PET scan will be obtained per discretion of the physician. Biopsy is recommended although will be at the discretion of treating physician. Treatment after failure will be at the treating teams discretion and documented.

11.2.3 QOL assessments will be made using the FACT-L questionnaire. Questionnaires will be given every 6 months for 2 years.

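### Section 12.2 names a 3-month adverse event rate, but the visit schedule in 11.2.1 has no toxicity evaluation at which to measure it

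*Combined protocol and SAP*

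**What the plan says.** Section 12.2 (Primary Endpoint) names toxicity and quality of life as the primary aim and sets the times for the toxicity analysis: "Adverse event rates will be compared at specific time points (3, 6 and 12 months after completion of SBRT". It does not say whether each rate is a point rate at that time or cumulative up to it.

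Section 11.2.1 gives the visits: "Patients will be seen 4 to 6 weeks after the last fraction of radiation therapy, every 6 months for 2 years".

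In the 11.1 table, the row "Toxicity Evaluation" is marked under three columns:
- "During Therapy (each fraction", that is, each treatment session;
- "At 4-6 Weeks (+/- 1 month) after SBRT";
- the later-visit column, whose header reads "Every -6 months (+/- 1 month) after RT for 12years" in the text available and is plainly damaged.

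The Pre-Study Entry cell of that row is blank. The only item in section 11 tied to 3 months is a lung function test, which the 11.1 footnote and 6.8.5 both make optional.

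**The concern.** Toxicity is the primary endpoint, and 3 months is the only time in 12.2 earlier than 6 months. It is thus the one closest to the acute toxicity that 2.1.1 makes the primary objective. If no evaluation is scheduled near that time, a point rate at 3 months must be assembled from an earlier visit, from events patients happen to report, or from what they remember at the 6-month visit.

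The protocol's own account of timing makes this relevant. Section 6.8.2 expects pneumonitis weeks to months after treatment, and 6.8.4 expects chest wall pain several months after it.

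A smaller matter concerns the reference level. CTCAE grades have no designated baseline, and 3.1.6 admits patients already treated for lung metastases. In a single-arm study, cough, dyspnea, fatigue or pain present at entry may be counted as toxicity of SBRT.

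**Working it through.** **Inputs.** Analysis times of 3, 6 and 12 months (12.2). Visits at 4-6 weeks and every 6 months (11.2.1). Tolerance of one month either side (11.1). One month is taken as 365.25/12 = 30.44 days, and day 0 is the end of SBRT.

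**Permitted windows.**
- First follow-up: opens at 28 - 30.4 = -2.4, taken as day 0; closes at 42 + 30.4 = day 72.4.
- 6-month visit: 182.6 - 30.4 = day 152.2 to 182.6 + 30.4 = day 213.1.
- 12-month visit: day 334.8 to day 395.7.

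**Analysis times against the windows.**

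| Time in 12.2 | Day | In a permitted window? |
|---|---|---|
| 3 months | 91.3 | No |
| 6 months | 182.6 | Yes (152.2 to 213.1) |
| 12 months | 365.2 | Yes (334.8 to 395.7) |

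**Size of the gap.** The span with no permitted visit is 152.2 - 72.4 = 79.8 days. Day 91.3 falls 91.3 - 72.4 = 18.9 days after it opens and 152.2 - 91.3 = 60.9 days before it ends.

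**At nominal timing.** The first follow-up is at day 28 to 42, so 91.3 - 42 = 49.3 to 91.3 - 28 = 63.3 days before month 3 follow the last scheduled evaluation. That is 49.3/91.3 = 54% to 63.3/91.3 = 69% of the first three months.

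**Sensitivity.**
- Taking the tolerance as 28 or 31 days closes the first window at day 70 or day 73. Even with 3 months as short as 89 days, it lies 89 - 73 = 16 days outside.
- Counting the 6 months from the first follow-up instead of from the end of treatment, the earliest next visit is 0 + 182.6 - 30.4 = day 152.2, so nothing changes.

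**If a 3-month contact were added.** The interval to the 6-month visit would be 182.6 - 91.3 = 91.3 days at nominal timing and up to 213.1 - 91.3 = 121.8 days within the window.

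**What a telephone contact could find.** Appendix III lists 19 distinct toxicities. For 10 of them the lowest listed grade is asymptomatic: pneumonitis, atelectasis, bronchial obstruction, fistula and stricture, fracture, pericarditis, pericardial effusion, heart failure and myocardial infarction.

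**The case against.** **The 11.1 header may once have read differently.** A character seems to be missing before the hyphen, and a 3-to-6-month interval is conceivable. A reader might infer that 11.1 itself rules out a 3-month visit; the damaged text does not support that. The point rests on 11.2.1. Section 11.2.3 ("Questionnaires will be given every 6 months for 2 years") gives the same interval, but only for the FACT-L. If the header did allow 3 months, 11.1 and 11.2.1 would disagree and would still need reconciling.

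**Events between visits are not lost.** Section 6.8.2 has reported symptoms evaluated promptly. Section 6.9 requires all acute and late toxicity related to SBRT to be reported, and it suspends accrual for Grade 4 or 5 events possibly related to treatment. A reader might infer that early toxicity goes unrecorded; the documents do not support that, and a cumulative 3-month rate could be built from reported events. But 12.2 does not say the rate is cumulative, and events without symptoms need an evaluation to be found.

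**Little hangs on the 3-month figure.** No test, threshold or sample size in this 20-patient pilot depends on it. Late toxicity is secondary in 2.1.2, although 13.1 lists it with acute toxicity as primary, so late chest wall pain counts toward the primary endpoint only on some readings. This limits the consequence but does not remove the mismatch.

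**Entry symptoms are partly recorded.** The history and physical, Zubrod status and FACT-L are all marked at pre-study entry, and Table 4 grades lung function decline against the patient's own baseline. A reader might infer that no baseline of any kind exists; that goes too far. What is missing is a CTCAE grade at entry. The fraction-1 evaluation is neither placed before treatment nor named as baseline.

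**Conclusion.** The mismatch between 12.2 and 11.2.1 stands: one of the three named times for the primary endpoint has no scheduled toxicity evaluation. As a point rate, the 3-month figure cannot be obtained from the schedule; it would depend on unscheduled reports or recall at months 5 to 7. The other two times are covered. This assumes that 11.2.1 governs and that the tolerances in 11.1 apply to its visits; the result does not depend on the length taken for a month.

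It is worth correcting because it touches the primary endpoint, but it leaves the acute phase with data from each fraction and from the 4-6 week visit.

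The baseline matter is secondary. A reader might infer that toxicity rates will be materially inflated; the documents give no number of patients with symptoms at entry, so no size can be put on it.

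**What to change.** **Reconcile 12.2 with 11.1 and 11.2.1.** Preferably, replace the 3/6/12-month comparison with the worst CTCAE 4.0 grade per patient and its onset date, reported as:
- an early rate at the 4-6 week evaluation, with each patient's actual days of observation stated, since the window runs from day 0 to about day 72;
- cumulative rates from first fraction by 6 and by 12 months;
- exact 95% confidence intervals, with a stated denominator for patients who die or miss the visit.

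This adds no visit. It needs an onset date on the toxicity form; dates collected at 6 months are still recall, but no rate then depends on placing an event before or after day 91. It should not be assumed that a chest CT supports the early rate: 11.2.2 says "Prior to each visit, a CT of the chest with contrast will be obtained for disease assessment", while the CT row of 11.1 has no mark at 4-6 weeks.

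**If 3 months is kept,** schedule a toxicity contact then, at a cost of at most 20 contacts. State that a telephone contact finds symptomatic events only, and that the interval to the 6-month visit is still about 91 days nominally and up to about 122 days. In either case, confirm the later-visit header in 11.1 and make it and 11.2.1 agree.

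**Baseline.** In 11.1, mark Toxicity Evaluation under Pre-Study Entry, graded by CTCAE 4.0 at the history and physical already required. Report events rising above baseline beside the crude rate. The cost is a form entry. The above-baseline rate misses worsening within a grade, which is why the crude rate should stay.

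### Section 12.3 times disease-free survival from a randomization that does not occur, leaves PFS undefined and has a censoring rule that does not fit the patients; 12.4 gives local control no time point or estimator

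*Combined protocol and SAP*

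**What the plan says.** All of this is in section 12 of the combined protocol and SAP unless noted.

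- Design (12.1): "This is a non-randomized Phase II pilot protocol". The only entry step described is registration (5.0).
- Endpoints named (12.3): "The secondary objective of this study is to assess local and regional control, progression-free survival and overall survival".
- Endpoint defined (12.3): "Disease-free survival is defined as the time from randomization until documented disease-recurrence or death, whichever occurs first". No definition of PFS follows, although 12.1 and 12.4 also name it.
- Censoring (12.3): "Patients who are disease-free and alive at the time of analysis will be censored at the time of their last follow-up".
- Unit (12.3): "Local and regional recurrence will be defined for each lesion per criteria in section 11.3.2".
- Follow-up (12.3): "Patients will be followed for disease-free survival for a minimum of 3 years". Section 11.2.1 schedules six-monthly visits for 2 years.
- Analysis (12.4): "Crude rates of locoregional recurrences will be documented as well as the time to development of recurrence or relapse". The time of last follow-up or death is also noted, and the stated use is: "This will allow us to calculate progression free and overall survival rates".

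**The concern.** A survival endpoint needs an origin, an event and a censoring rule. Here the origin does not exist, the listed endpoint (PFS) differs in name from the defined one (disease-free survival), and the censoring sentence describes patients who have been cleared of disease. In this trial everyone enters with 1-5 lung lesions (3.1.4), and many may remain with visible tumor without having failed. Two analysts could start the clock at registration, first fraction or last fraction, and could handle a living patient with stable disease differently, possibly after seeing the data.

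For local control, a crude proportion with no time point mixes the failure rate with length of follow-up and with deaths before failure. Section 1.0 gives documenting local control as a purpose of the study and cites 2-year control figures of 77.9%, 88% and 96%. A crude rate is not directly comparable with those.

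**Working it through.** **Wording checks**

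1. Origin. Section 12.1 (non-randomized) and 5.0 (registration only) rule out the origin given in 12.3. No other origin is stated for disease-free survival, PFS or OS.
2. Endpoint. PFS and disease-free survival may be one endpoint under two names, but the text does not say so.
3. Censoring. Section 11.3.2 defines partial response and stable disease; neither is a recurrence and neither is disease-free. Section 11.3.1 has indeterminate consolidation treated as residual tumor. Under 11.3.2, Local Enlargement counts as tumor failure only with PET or biopsy confirmation, and 11.2.2 leaves both to the physician. A living patient in any of these states without a confirmed failure has, literally, neither an event nor a censoring rule.

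The documents give no expected counts for these states, so no size is attached to points 1-3.

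**Crude rate: illustration**

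The plan has no figure of its own to reproduce. Inputs from section 1.0: 2-year local control LC of 77.9%, 88% and 96%; 2-year survival S of 32% to 87%. The schema gives 40 tumors.

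Assumptions: each LC is net control (the documents do not say how it was estimated); failure and death times are independent and exponential; all follow-up is capped at t. The 3-year case extends the 2-year hazard and assumes failures are still detected after the 11.2.1 visits end.

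- Failure hazard hf = -ln(LC)/2: 0.1249, 0.0639 and 0.0204 per year.
- Death hazard hd = -ln(S)/2: 0.5697 (S = 32%) and 0.0696 (S = 87%) per year.
- 1 minus Kaplan-Meier at 2 years = 1 - LC.
- Expected crude failure = hf/(hf+hd) × (1 - exp(-(hf+hd)t)).

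Worked case, LC 77.9%, t = 2:

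- S = 32%: 0.1249/0.6946 × (1 - 0.779 × 0.32) = 0.180 × 0.751 = 0.135.
- S = 87%: 0.1249/0.1945 × (1 - 0.779 × 0.87) = 0.642 × 0.322 = 0.207.

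| LC | 1 - KM, 2 y | Crude, 2-y cap | Crude, 3-y cap | Crude failures of 40 (2-y; 3-y) |
|---|---|---|---|---|
| 77.9% | 22.1% | 13.5-20.7% | 15.7-28.4% | 5.4-8.3; 6.3-11.4 |
| 88% | 12.0% | 7.2-11.2% | 8.6-15.8% | 2.9-4.5; 3.4-6.3 |
| 96% | 4.0% | 2.4-3.7% | 2.9-5.4% | 1.0-1.5; 1.1-2.1 |

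With the same underlying control, the crude rate can read below or above the 2-year figure. The largest shortfall at the 2-year cap is 22.1 - 13.5 = 8.6 points for 77.9%, 12.0 - 7.2 = 4.8 for 88%, and 4.0 - 2.4 = 1.6 for 96%.

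**Unit.** Recurrence is defined per lesion. The schema implies 40/20 = 2 lesions per patient on average, and nothing is said about correlation within a patient.

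**The case against.** The strongest reply is that these are wording slips in secondary measures of a 20-patient pilot with no hypothesis test. PFS and disease-free survival are absent from the secondary objectives in 2.1.2 and the secondary endpoints in 13.2. That stands, and it limits the weight of the point.

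Some stronger readings are tempting but are not supported:

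- A reader might infer that recurrences are undated or that a crude rate is all that will be available. Section 12.4 also documents time to recurrence and time of last follow-up or death. What is missing is a landmark time, an estimator for local control and a rule for deaths before failure.
- A reader might infer that no unit is given. Section 12.3 defines recurrence for each lesion; the gap is clustering.
- A reader might infer that disease-free survival cannot be computed. Taking disease-free to mean event-free makes the rule workable, and 12.4 notes last follow-up without restricting it to disease-free patients. That is probably the intent, but it has to be inferred.
- A reader might infer that there is nothing to set a crude rate against. Section 1.0 also cites crude local control of 67-100%. That range is wide and carries no follow-up time, so the difficulty with the 2-year figures remains. The plan states no formal comparison with any of them.

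The illustration is also open to challenge. If a cited figure is itself crude, the gap does not apply to it. For 88%, the sarcoma-specific figure, the 2-year-cap gap is at most 4.8 - 2.9 = 1.9 tumors of 40. The sampling half-width at 12% is 1.96 × √(0.12 × 0.88/40) = 0.10, or about 4 tumors, before clustering. That argues against overstating the size, but not against naming a time point and an estimator.

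The follow-up duration in the 11.1 table may be garbled text and is not relied on.

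**Conclusion.** The concern holds in this form. Section 12.3 uses an origin that the design lacks and supplies no other, leaves PFS undefined, and has a censoring sentence that, read literally, does not cover living patients with residual disease and no recurrence. Section 12.4 leaves local control without a landmark time, an estimator or a treatment of death before failure, and clustering of lesions is not addressed. The 3-year minimum in 12.3 also exceeds the 2 years of visits in 11.2.1.

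Only the crude-rate part is sized: 22.1% against 13.5-20.7% or 15.7-28.4% for 77.9% control, and less for 88% and 96%. This rests on net control, independent exponential times and 32-87% 2-year survival. The measures are secondary and descriptive, and the primary toxicity objective is unaffected. The text should be corrected because the repair is cheap and removes choices that could otherwise be made after the data are seen.

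**What to change.** **Section 12.3.** Replace disease-free survival with a single PFS endpoint. Start it at a date that exists, either registration or the first SBRT fraction, stated once and used for OS as well. The event is the first of local failure per 11.3.2, documented progression elsewhere, or death. Censor every living patient without such an event at the last disease assessment, whatever the response state, including unconfirmed Local Enlargement. Use Kaplan-Meier for PFS and OS.

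**Section 12.4.** Report 1- and 2-year cumulative incidence of local failure with death as a competing event, plus Kaplan-Meier local control for reading alongside the cited 2-year figures. Cluster any per-lesion intervals by patient. Keep the crude rate as a descriptive figure with its follow-up stated.

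**Follow-up.** Reconcile the 3-year minimum in 12.3 with the 2 years of visits in 11.2.1.

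**Cost.** Revised wording and a little more analysis; dates of recurrence, last follow-up and death are already to be recorded. Two limits remain. Only chest CT is scheduled, so extrathoracic progression enters PFS only as clinically detected. Censoring unconfirmed Local Enlargement follows 11.3.2 but may leave some true failures uncounted or counted late.

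### DFS and PFS are censored at an undefined last follow-up, so disease-free time is credited after chest CTs stop, most clearly between the 2-year end of visits and the 3-year DFS follow-up

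*Combined protocol and SAP*

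**What the plan says.** Section 12.3 defines the endpoint: "Disease-free survival is defined as the time from randomization until documented disease-recurrence or death, whichever occurs first". It then gives the censoring rule: "Patients who are disease-free and alive at the time of analysis will be censored at the time of their last follow-up". The same section sets a minimum of 3 years of follow-up for DFS. Last follow-up is not defined anywhere in the document.

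Section 12.4 records one date for two endpoints: "Time of last follow-up or death will also be noted. This will allow us to calculate progression free and overall survival rates".

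On assessments, 11.2.1 says "Patients will be seen 4 to 6 weeks after the last fraction of radiation therapy, every 6 months for 2 years", and 11.2.2 says "Prior to each visit, a CT of the chest with contrast will be obtained for disease assessment". The table in 11.1 gives another duration, "Every -6 months (+/- 1 month) after RT for 12years", which may be a typing or text-conversion fault. That table marks no CT at the 4-6 week visit.

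**The concern.** The date last known alive is the right censoring date for overall survival. It is not right for an endpoint whose event must be documented, because a patient can be known to be alive while nobody has looked for recurrence. In this study the looking is mainly by imaging: 11.2.2 makes the chest CT the disease assessment, and 11.3.2 defines local failure by measured enlargement with PET or biopsy support.

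Wherever last contact falls later than the last assessment, the interval between them enters the risk set as disease-free time with little chance of an event. The error runs one way: the estimated recurrence-or-death rate goes down and the DFS/PFS curve goes up. A single-arm study has no control arm in which the same error could cancel. Section 12.1 names progression-free survival as a measure of disease control, so the curve is likely to be reported and set against other series.

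**Working it through.** The plan states no DFS or PFS rate, event count or hazard, so there is no design figure to reproduce. The check uses schedule arithmetic and then an illustrative model.

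**1. How long can the unimaged interval be?**
- Last follow-up is a scheduled visit with its CT (11.2.2): about 0 months.
- Contact falls between two scheduled CTs: up to about 6 months, or 8 with the ±1 month windows.
- CTs end at month 24 (11.2.1) and DFS is followed to month 36 (12.3): 36 − 24 = 12 months, at least, for every recurrence-free survivor.

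**2. Model.** All of the following are assumptions.
- Recurrence is exponential with median 12 months: r = ln 2/12 = 0.0578 per month.
- Death before recurrence: d = 0.003 per month.
- Median 15 months from recurrence to death: m = ln 2/15 = 0.0462 per month.
- Recurrence is found only on a CT at month 6, 12, 18 or 24.
- Contact continues to month 36.

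True DFS at a CT time t is S(t) = exp[−(r+d)t]. This gives S(24) = 23.3% and S(36) = 11.2%.

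The chance that a patient who is recurrence-free at the last CT is alive t months later, whether or not an unseen recurrence has occurred, is

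A(t) = exp[−(r+d)t] + r/(r+d−m) × {exp(−mt) − exp[−(r+d)t]}.

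This gives A(12) = 0.848.

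**3. Month 36, no missed CTs, CTs end at month 24.** Under the rule as written, such a patient stays event-free unless he or she dies: S(24) × A(12) = 0.2326 × 0.848 = 19.7%, against a true 11.2%. A simulation of 40,000 patients gave 19.5% against 11.0%, an excess of 8.5 points.

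**4. Month 24.** With full CT compliance the rule returns S(24) itself, so the bias is zero. Now let a fraction p stop CT, with the last CT equally likely at month 0, 6, 12 or 18, and stay in contact. Their apparent 24-month DFS, S(c) × A(24−c), is 61.9%, 50.9%, 40.9% and 31.7%, with mean 46.3%.
- p = 15%: 0.85 × 23.3 + 0.15 × 46.3 = 26.7%, an excess of about 3.5 points (simulation 26.6%).
- p = 30%: 0.70 × 23.3 + 0.30 × 46.3 = 30.2%, an excess of about 7 points (simulation 30.5%).

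Over recurrence medians of 9 to 18 months the excess stays at about 3 to 7 points. Censoring at last CT in the same simulations gave 23.7% and 24.7%, close to the true value.

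**5. A second simulation with other assumptions.** It used recurrence medians of 12, 24 and 36 months, death medians of 36 or 60 months, and 4,000 patients per scenario. The first three rows show DFS with last-contact censoring minus DFS with last-CT censoring.

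| Scenario | Month | Difference (points) |
|---|---|---|
| CTs to month 24, none missed, 0 or 10% per year lost | 24 | 0.5 to 1.8 |
| CTs to month 24, 20% missed, 10% per year lost | 24 | 3.3 to 3.9 |
| CTs continue throughout, none missed, 10% per year lost | 12, 24, 36 | 0.6 to 1.1 |
| Last-contact censoring only: CTs ending at month 24 minus CTs continuing (12.8 v 7.8; 25.7 v 20.4; 42.4 v 34.9), 10% per year lost | 36 | 5.0, 5.3, 7.5 |

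**6. Does moving the censoring date repair month 36?** No. With CTs ending at month 24 and no losses, last-CT censoring gave 5.9%, 12.3% and 20.4% at month 36, against true values of 6.2%, 17.7% and 33.0%. After the last CT only deaths remain as events, and the survivors have left the risk set. The estimate has to stop where the imaging stops.

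**7. Precision.** With 20 patients and DFS near 25%, the 95% half-width is 1.96 × √(0.25 × 0.75/20) = 19 points. One patient is 5 points.

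**The case against.** The strongest reply is that follow-up in this protocol means clinic visits, and 11.2.2 puts a chest CT before each one. On that reading last follow-up and last CT nearly coincide, apart from the 4-6 week visit, and the rule is harmless through month 24. This stands. The 24-month excess rests wholly on assumed patients who stop scanning but remain in contact. The documents give no missed-scan rate and describe no survival-only contact.

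The reply does not cover months 24 to 36. Section 12.3 requires DFS follow-up that 11.2.1 does not supply with visits or CTs, and the duration in the table of 11.1 cannot be relied on to fill the gap.

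A reader might go further and infer that the rule makes DFS/PFS overstated at every time point, or that no recurrence can be recorded once scans stop. The documents support neither. The event in 12.3 is documented recurrence, not recurrence on CT. History and physical are scheduled at follow-up visits, PET/CT is available if needed, and biopsy can confirm failure. If half of recurrences surfaced clinically with a mean delay of 4 months (an assumption), the 24-month excess would fall from about 3.4 and 7.0 points to about 2.1 and 4.3.

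Nor should all unimaged person-time be put down to patients who stop scanning. In the first model, 21% to 36% of DFS person-time lies after the last CT when 15% to 30% stop, but 11% to 20% does so when nobody stops. That part is the tail from month 24 to 36, and reconciling the schedule could remove it.

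**Conclusion.** The concern holds in a conditional form. The censoring date is undefined and shared with overall survival. It does no material harm through month 24 if CTs are done as planned. It tends to overstate DFS/PFS after missed CTs and, on a literal reading of 11.2.1 with 12.3, over at least 12 months after the last scheduled CT.

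Under the assumed 12-month recurrence median and CT-only detection, the size is zero at month 24 with full compliance, about 3 to 7 points with 15% to 30% stopping CT, and about 8 points at month 36. These are upper-end values because some recurrences will surface clinically. They amount to roughly one or two patients in 20 and lie within sampling error, though they run in one direction.

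Severity is low. DFS/PFS is a secondary endpoint in 12.3 with no test or benchmark, it is not listed in 2.1.2 or 13.2, and the primary objective concerns toxicity. This is a cheap improvement.

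**What to change.** In 12.3, replace the censoring sentence with wording such as: For DFS and PFS, patients alive without documented recurrence are censored at their last adequate disease assessment (normally the last chest CT; start of SBRT if there is none). Death without recurrence remains an event. DFS and PFS are not reported beyond the imaged period. For overall survival, living patients are censored at the date last known alive.

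The term adequate disease assessment is better than chest CT alone, because a chest CT does not establish freedom from recurrence outside the lungs.

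In 12.4, record the date of the last disease assessment separately from the date of last contact. Reconcile the follow-up durations in 11.1, 11.2.1 and 12.3; the sponsor must decide which is intended.

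The cost is a few sentences and one date that should already be in the imaging record. The censoring change itself adds no scans, visits or patients. The drawbacks are less DFS/PFS follow-up time, a slightly less favourable estimate, and a small residual bias, because deaths after the last scan still count while survivors are censored earlier. In the simulations the largest departure from the true 24-month value after the change was 1.9 points (16.7% against 14.8%, recurrence median 9 months, 30% stopping CT).
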